**Efficacy Analyses**

The continuous and ordinal efficacy variables collected at each visit (and time point, where relevant) will be summarized with number of observations (n), mean, standard deviation, median, minimum and maximum. Statistical inference testing will be conducted and the results will be utilized as additional descriptors of the data. Two-sample *t*-tests will be employed for continuous variables. Two-sample *t*-tests, Wilcoxon rank sum tests and analysis of covariance (ANCOVA) models adjusting for baseline will be employed for ordinal variables. For the ANCOVA models, treatment will be compared to the placebo. Pearson's chi-square or Fisher's exact tests (in the case of expected counts less than 5) will be employed for qualitative variables. Where appropriate, the change from baseline for each parameter will also be summarized using descriptive statistics.

The individual symptoms collected in the diary will be analyzed including all data across the 70-day treatment period, testing for a treatment effect using a generalized linear model that accounts for repeated measures with an unstructured correlation structure, including terms for diary day and the treatment-by-day interaction.

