### 2.1 Study Variables

### 2.2 Efficacy Variables

The key efficacy variables include the following:

- GLIA Ocular Surface Disease Questionnaire taken at the clinic
- Modified Symptom Assessment in Dry Eye Questionnaire (SANDE) taken at the clinic

Additional efficacy variables include the following:

- Chronic Ocular GvHD Signs including the following:
  - TearScan Examination
  - Visual acuity with current correction
  - Slit lamp biomicroscopy without staining:

- Lid Edema, Lid Erythema, Lid Margin Ulceration and Conjunctival Hyperemia are of interest however all ocular regions will be analyzed similarly
  - Corneal and conjunctival fluorescein staining
  - Facial Presentation and Blinks per Minute
- Daily diary GLIA Ocular Surface Disease Questionnaire
- Daily use of eye drops
- National Institutes of Health (NIH) Eye Score

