#### 5. Sample Size and Power Considerations

This study will randomize 33 subjects (22 to Pro-ocular™ 1% topical gel, and 11 to Placebo).

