### 13.1.1 ANALYSIS OF GLIA OCULAR SURFACE DISEASE SYMPTOMS QUESTIONNAIRE COLLECTED IN CLINIC

#### The primary analysis (Study Treatment Phase):

For each symptom, an analysis of covariance (ANCOVA) will be used to compare change from baseline between Pro-ocular and placebo with adjustments for baseline symptom score (BASELINE), treatment group (TRT), visit (VISIT), and treatment x visit interaction (TRT\*VISIT) as the explanatory variable. The least squares (LS) means, LS mean differences, SEs, two-sided 95% CIs for the difference in LS means, and two-sided p-values (unadjusted and Benjamini-Hochberg adjusted p-values) will be reported for the treatment effect at each visit and all visits combined. Model effects will also be displayed.

SAS pseudo-code for this model follows:

```
PROC MIXED data=indata order=internal;
  By EYETYPE;
  class TRT VISIT;
  model CFB = TRT BASELINE VISIT TRT*VISIT;
  LSMEANS TRT VISIT TRT*VISIT / CL PDIFF;
run;
```

The ITT population will be used as the primary population using LOCF for imputation.

Sensitivity analyses will include the ITT population and PP population using observed cases.

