### **13.1.2 Analysis of GLIA Ocular Surface Disease Symptoms Questionnaire Collected in Daily Diary**

The individual symptoms collected in the diary will be analyzed including all data across the 70-day treatment period, testing for a treatment effect using a generalized linear model that accounts for repeated measures, with an unstructured correlation structure, including terms for diary day. The LS means, LS mean differences, SEs, two-sided 95% CIs for the difference in LS means, and two-sided p-values will be reported. Model effects will be presented.

SAS pseudo-code for this model follows:

```
PROC MIXED data=indata order=internal;
  class TRT;
  model SYMPTOM = TRT DAY;
  repeated / subject=SUBJ type=UN ;
  random DAY;
  LSMEANS TRT / CL PDIFF;
run;
```

The LS mean (and SE) daily scores will be displayed graphically by treatment group across the 70 days. The mixed effects model analyses will be truncated at Visit 5 and any data presented after Visit 5 will be summarized with continuous descripted statistics.

Individual subject plots will also be presented displaying the subject score by day.

Analyses will be performed on the ITT population using observed cases only.

All Symptom scores collected via diary will be presented in a subject listing.

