## 16. Changes from Protocol-Stated Analyses

The protocol and SAP call for LOCF imputation and for sensitivity analyses in the Per Protocol population for the key efficacy endpoints. Given there is only 1 early discontinuation and no expected major protocol deviations, the LOCF imputation and Per Protocol population have been removed due to the expected similarity with the ITT Population using only observed data. The protocol calls for t-tests and ANCOVA analyses for ordinal data, It has been decided that the Wilcoxon Rank Sum Test will be sufficient and the t-test and ANCOVA will not be done.

All crossover data collected will be summarized with continuous descriptive statistics or with counts and percentages as appropriate.

Interblink interval may appear in the protocol however all instances of interblink interval have been changed to Facial Presentation and Blinks per Minute

Per the Sponsor an additional ANCOVA model including eye type has been added for the key efficacy variables.

Additional exploratory analyses may be requested after final analyses and may be detailed in the clinical study report.

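### The daily-diary model in SAP 13.1.2 cannot be fitted as written (unstructured covariance over about 70 days from 33 subjects, no fallback), and it has no treatment-by-day term

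*SAP*

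**What the plan says.** SAP Section 13.1.2 models every diary day of the 70-day treatment period with a repeated-measures model. The text asks for an unstructured correlation structure, and the PROC MIXED pseudo-code agrees: "repeated / subject=SUBJ type=UN". Only treatment is a CLASS variable. The fixed effects are treatment and day, the only LS means requested are for treatment, and a `random DAY` statement has no SUBJECT= option. The planned display is more detailed: "The LS mean (and SE) daily scores will be displayed graphically by treatment group across the 70 days". On the end of the modelled period, the section says "The mixed effects model analyses will be truncated at Visit 5". It uses observed cases only and gives no alternative structure or rule for non-convergence.

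Elsewhere:
- SAP Section 5: "This study will randomize 33 subjects" (22 and 11).
- SAP Section 13.1.1, same questionnaire in clinic: "model CFB = TRT BASELINE VISIT TRT*VISIT", which does include treatment by time.
- SAP Section 2.2 lists the "Daily diary GLIA Ocular Surface Disease Questionnaire" among the additional variables, not the key ones.
- SAP Section 16, on follow-up: "Given there is only 1 early discontinuation and no expected major protocol deviations".
- Protocol Section VI, on the role of the tests: "Statistical inference testing will be conducted and the results will be utilized as additional descriptors of the data". Its diary model is also unstructured, but with a treatment-by-day interaction. SAP Section 1 states that the SAP's methods supersede the protocol's.

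**The concern.** An unstructured matrix over 70 days needs well over 70 subjects' worth of information, and the trial has 33. If the fit fails, the planned treatment test for all 15 diary symptoms has no specified form. The replacement would then be chosen without a rule, possibly with treatment codes in hand, and plausible replacements differ widely in how well they hold the error rate.

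Separately, the plot promises daily means by arm, but the model lets the arms differ only by a constant. An effect that builds up or fades would be averaged away.

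**Working it through.** **Inputs.** n = 33 (SAP Section 5). T = 70 diary days, or 67 to 73 with the Visit 5 window of Day 70 ± 3 (SAP Table 1). Coded mean: treatment plus linear day. The SAP gives no parameter count or power figure to reproduce; 22 + 11 = 33 agrees.

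**1. Parameters against data**, per symptom and eye type, T(T+1)/2 against nT:

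| T | Covariance parameters | Values at most |
|---|---|---|
| 67 | 2,278 | 2,211 |
| 70 | 2,485 | 2,310 |
| 73 | 2,701 | 2,409 |

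**2. Rank.** Thirty-three residual vectors span at most 33 of 70 dimensions. Simulated data gave rank 33 with the coded mean and 31 with a free mean for each arm and day. At least 70 − 33 = 37 directions carry no residual variation.

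**3. Unbounded likelihood.** Shrinking the variance in those directions raises the log-likelihood without limit. Each tenfold drop adds 33 × 37 / 2 × ln 10 = 1,406. A REML evaluation on a stricter set of 35 directions (also orthogonal to the intercept and day) rose from −2,038 to −708, 622, 3,281 and 5,941 as the variance fell from 1 to 0.1, 0.01, 10⁻⁴ and 10⁻⁶. That is 33 × 35 / 2 × ln 10 = 1,330 per tenfold drop.

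**4. Missed days.** With 20% of days missing at random, the log-likelihood was −1,794, −915, 841 and 2,598 at variances 0.1, 0.01, 10⁻⁴ and 10⁻⁶, about 879 per tenfold drop. This is as expected: about 56 observed days per subject leave 56 − 33 = 23 such directions, and 33 × 23 / 2 × ln 10 = 874.

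**5. Mean model.** Three free parameters (intercept, treatment, slope) describe all 2 × 70 = 140 daily means. `LSMEANS TRT` returns one mean per arm. Evaluated by day, the code gives two parallel straight lines. Illustration (assumed): if the true difference grew linearly from 0 on Day 1 to 2 points on Day 70, the model would show about (0 + 2) / 2 = 1 point on every day.

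**6. `random DAY`.** Without SUBJECT= its column equals the fixed day column. The design has rank 3 with or without it, so it adds no subject-specific slope.

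**7. Does the replacement matter?** Simulated false-positive rate at nominal 5%: no treatment effect, 22 against 11, 70 complete days, REML, treatment plus linear day, t with 31 df, 2,000 runs per row. All variance inputs are assumptions; residual SD is 1.5 throughout.

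| Subject SD | Day-to-day correlation | Slope SD per day | AR(1) alone | Compound symmetry | Random intercept + AR(1) |
|---|---|---|---|---|---|
| 1.5 | 0.6 | 0 | 36.5% | 5.0% | 5.1% |
| 1.0 | 0.6 | 0 | 32.0% | 5.9% | 6.1% |
| 2.0 | 0.6 | 0 | 34.8% | 5.8% | 5.6% |
| 1.5 | 0.8 | 0 | 23.0% | 4.3% | 4.4% |
| 1.5 | 0.6 | 0.02 | 34.8% | 5.8% | 5.6% |

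In the first row the true SE is √[(1.5² + 1.5² × mean AR(1) correlation) × (1/22 + 1/11)] = 0.569, while AR(1) alone reports 0.260 on average.

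**8. Weekly means.** Ten weeks need 10 × 11 / 2 = 55 parameters, and 33 subjects give full rank (10 of 10). With 20% missed days, one dropout, Visit 5 on Days 67 to 73 and at least 3 diary days per weekly mean, the average-over-weeks test rejected in 5.5% (no slope) and 6.1% (slope SD 0.02) of 1,000 runs each, using t with 31 df. All 2,000 fits converged.

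**The case against.** The strongest reply concerns weight. The diary appears in neither hypothesis of SAP Section 2.5, the multiplicity procedure covers only the key variables, and the protocol treats its tests as descriptive. A failed fit would be seen, and the individual daily plots and listings would survive it. That stands, and it limits the priority.

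Several stronger readings are tempting, and the documents do not support them:
- A reader might infer that any unstructured estimate is limited to rank 33. The bound belongs to the likelihood fit that PROC MIXED performs. With missed days, a pairwise moment estimate can reach rank 70; in one trial run it did, with a negative smallest eigenvalue (about −4.8), so it was unusable for another reason.
- The straight lines rest only on DAY being absent from CLASS in what the SAP labels pseudo-code. The text's diary-day terms could mean categorical days. The missing treatment-by-day term does not depend on this: it is absent from both text and code.
- The omitted interaction might look like an undisclosed change. The SAP was written for protocol version 4.0, which is not supplied; the interaction is in version 5.1. No such claim can be made.
- The diary code has no eye-type statement, but SAP Sections 8.1 and 13 and the by-eye diary table already require separate eyes. A model for the combined-eyes diary table is still not given, a secondary gap.
- REPEATED names no effect, so records would be misplaced only if missed days are absent rows. The SAP does not say how they are stored.

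**Conclusion.** The point holds. As written, the diary treatment test cannot be run for any of the 15 symptoms, across the whole Visit 5 window and with 20% of diary days missed. Dropout does not change this, since the SAP reports one early discontinuation. The model also cannot show a treatment difference that varies over the 70 days.

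The consequence is limited to an additional efficacy variable; the key clinic GLIA and SANDE analyses are unaffected. It should be corrected before unmasking because the choice of replacement is not neutral.

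A reader might take 23% to 37% as the SAP's false-positive rate. It is not: the SAP never names AR(1) alone, and the figure illustrates one poor replacement under assumed variances, with data generated from a random intercept plus AR(1) (one case adds a slope). Compound symmetry held its level in the same runs. The rank and parameter counts need no such assumptions.

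**What to change.** Before treatment codes are released for the primary analysis, replace the model with one estimable model for all 15 symptoms, by eye type as Sections 8.1 and 13 already require. Choose one:

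- **(a) Weekly means.** Fixed effects TRT, WEEK and TRT*WEEK, with REPEATED WEEK / SUBJECT=SUBJ TYPE=UN (55 parameters). Use a single week definition shared with Section 13.3, after correcting its day count: there, Day 2 of Week 1 is first dosing day + 1 but Day 7 is + 7, where the same count gives + 6. Say where days after Day 70 and before Visit 5 belong.
- **(b) Daily data.** DAY as a class effect with TRT*DAY, a subject random intercept, and REPEATED DAY / SUBJECT=SUBJ TYPE=AR(1). The simulations above used a linear day, so this exact mean model was not simulated.

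In either case:
1. Remove `random DAY`.
2. Name the treatment difference averaged over time as the one test per symptom.
3. Take the plotted LS means from the treatment-by-time term.
4. State one fallback structure that includes a subject effect; AR(1) without one should not be used.
5. List the change in SAP Section 16.

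The cost is SAP wording and code, with no new data. Under (a) the modelled plot is weekly rather than daily; individual daily plots and listings stay.

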### **13.2 Modified SANDE – Symptom Assessment iN Dry Eye Questionnaire**

The Modified SANDE – Symptom Assessment iN Dry Eye Questionnaire will be collected at Visit 1 and Visits 3 – 7.

A VAS will be used to assess subject's symptoms, by eye, for the following:

- Frequency of Symptoms
- Severity of Symptoms

First, the subject will be asked to place a vertical line to indicate how often, on average, their eyes feel dry and/or irritated. For frequency, the VAS ranges from Rarely to All the Time.

Second, the subject will be asked to place a vertical line to indicate how severe, on average, they feel their symptoms of dryness and/or irritation are. For severity, the VAS ranges from Very Mild to Very Severe.

The result (in mm) will be measured from the left endpoint to the slash marked by subject on the line.

For each symptom, a score is derived by converting the measure length to a maximum score of 100 with one decimal place as follows:

$$\text{Score} = \text{Measured Result (mm)} * 100 / \text{CRF Scale Length (mm)}$$

The total SANDE score is calculated by multiplying the frequency of symptoms score with the severity of symptoms score and obtaining the square root.

Subjects whose values are all 0 for a given symptom for all visits will not be included in the analysis for that symptom

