Measures Taken to Reduce Bias:	Randomized treatment assignment; double-masked parallel study design, 2:1, study drug: placebo, 22 subjects:11 subjects
Number of Subjects:	33 patients diagnosed with chronic ocular GvHD in at least one eye, not wearing scleral or contact lens for at least one month in any eye prior to screening
Number of Study Sites:	1
Inclusion Criteria:	
 
1. Male or female of any race, at least 18 years of age at Visit 1 Screening.
 
2. Has the diagnosis of chronic ocular GvHD.
 
3. Has the NIH Consensus Eye Score of at least 2.
 
4. On the GLIA Ocular Surface Disease Symptoms Questionnaire at Screening, has ocular discomfort at a severity score of moderate or more, and at least one other symptom at a severity of moderate or more.
 
5. One or more signs from the list of chronic ocular GvHD signs below.
 
6. Has provided verbal and written informed consent.
 
7. Be able and willing to follow oral and written instructions, including participation in all study assessments and visits.
 

Exclusion Criteria:	
 
1. Wearing scleral lens within the last month, or those who plan to start wearing scleral lens during the study.
 
2. Anticipate major changes in systemic GvHD management during study period.
 
3. Comorbidity with other severe or chronic eye conditions that in the judgment of the investigator will interfere with study assessments, such as but not limited to retinal detachment, recent ocular surgery, Bell's palsy, active trigeminal neuritis or neuralgia.
 

	
 
4. Anticipate change of vision correction or anticipate any ocular procedure during study period.
 
5. A woman who is pregnant, nursing an infant, or planning a pregnancy.
 
6. A woman of childbearing potential who has a positive urine pregnancy test at Visit 1, or who does not use an adequate method of birth control throughout the study period.
 
7. Has a known adverse reaction and/or sensitivity to the study drug or its components.
 
8. Unwilling to cease the use of sunscreen on the forehead or eye area.
 
9. Intraocular pressure >22 mm Hg at screening visit with or without ongoing glaucoma treatment.
 
10. Currently enrolled in an investigational drug or device study for ocular GvHD.
 

--	--

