## 7. Analysis Populations

### 7.1 Modified Intent-to-Treat

The modified intent-to-treat (ITT) population includes all randomized subjects who received at least 1 application of the study drug. Subjects will be analyzed as randomized.

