### 13.2.1 Analysis of SANDE Questionnaire

The primary and additional analyses for the modify SANDE Questionnaire will be the same as the Glia Ocular Surface Disease Symptoms Questionnaire. Both ANCOVA analyses will be truncated at Visit 5 and any data presented after Visit 5 will be summarized with continuous descripted statistics.

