### 13.5.3 Slit Lamp without Staining

Slit lamp biomicroscopy examinations without staining will be performed at Visit 1 and Visits 3 – 7. The exam will assess the following components, by eye:

- Lids (erythema, edema, lid margin ulceration, lid margin notches, entropion/ ectropion, trichiasis/madarosis, floppy eyelids, hordeolum (stye))
- Conjunctiva (hyperemia, cicatricial changes, pseudomembranes, chalasis)
- Cornea (edema, corneal ulcers, filamentous keratitis, corneal thinning, corneal neovascularization, scars, conjunctival epithelium invasion, limbal thickening)
- Anterior Chamber (cells, flare)
- Lens (status, opacity)

A VAS ranging from None to Most will be used to score each component except for Lens.

The Investigator will mark a vertical slash on the VAS to indicate the level of severity.

The result (in mm), will be measured from left endpoint to the slash marked by the Investigator on the line.

For each component, a score is derived by converting the measure length to a maximum score of 10 with one decimal place as follows:

$$\text{Score} = \text{Measured Result (mm)} * 10 / \text{CRF Scale Length (mm)}$$

The Investigator will classify any abnormal results as Abnormal Clinically Significant (CS), or Abnormal Not Clinically Significant (NCS), including any other pathologies noted by the Investigator.

The Lens status will be classified as Phakic, Pseudophakic or Aphakic. For Phakic lens, the Lens Opacity will be scored as 0, +1, +2, or +3.

All continuous slit-lamp measures will be analysed the same as Glia Ocular Surface Disease Symptoms Questionnaire and the modified SANDE Questionnaire with the following exceptions. Only the ITT populations using observed cases will be performed and no adjustments for multiplicity will be applied.

The abnormal findings will be summarized using counts and percentages for each treatment group at each visit for each eye. Percentages will be based on the number of subjects in each treatment group with responses. Shift tables will also be provided comparing each follow-up visit to baseline.

During the Study Treatment Phase, the changes (or shifts) from baseline will be relative to the Study Treatment Phase baseline. During the Placebo Cross-over Phase, the changes (or shifts) from baseline will be relative to the Placebo Cross-over Phase baseline.

Analyses will be performed on the ITT population using observed data only.

All slit lamp results will be presented in a subject listing.

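### The SANDE rule that drops subjects scoring 0 at every visit selects on post-randomisation outcomes; it matters if applied per eye or carried over to the slit-lamp measures

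*SAP*

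**What the plan says.** The scoring section for the modified SANDE (SAP 13.2) ends with the exclusion: "Subjects whose values are all 0 for a given symptom for all visits will not be included in the analysis for that symptom". On timing, the same section says: "The Modified SANDE – Symptom Assessment iN Dry Eye Questionnaire will be collected at Visit 1 and Visits 3 – 7". Only the Visit 1 value precedes randomised treatment.

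The model comes from SAP 13.2.1: "The primary and additional analyses for the modify SANDE Questionnaire will be the same as the Glia Ocular Surface Disease Symptoms Questionnaire". That means the baseline-adjusted ANCOVA of change, run by eye type, plus an additional ANCOVA with an eye-type term and two-sample t-tests on change. SAP 8.1 and 13 require results for the worse eye, the fellow eye and all eyes combined.

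SAP 7.1 puts every randomised subject who received at least one application into the modified ITT population and mentions no score-based exclusion. SAP 16, which lists departures from the protocol's analyses, does not mention the rule.

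For the slit lamp, SAP 13.5.3 says: "All continuous slit-lamp measures will be analysed the same as Glia Ocular Surface Disease Symptoms Questionnaire and the modified SANDE Questionnaire with the following exceptions". The exceptions are: "Only the ITT populations using observed cases will be performed and no adjustments for multiplicity will be applied". The zero rule is not among them.

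The Protocol Synopsis plans for "33 patients diagnosed with chronic ocular GvHD in at least one eye", so a fellow eye may be free of disease.

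**The concern.** An exclusion fixed before treatment is harmless to the randomised comparison. This one is not fixed until follow-up is complete. Among subjects at 0 at baseline, those who stay at 0 leave the analysis and those who develop a symptom or sign remain. If treatment affects onset, the two arms lose different kinds and numbers of subjects. Even if it does not, removing subjects whose change is exactly 0 alters the mean change being estimated.

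The dropped values are genuine measurements. The left anchors of the SANDE lines are *Rarely* and *Very Mild*, so 0 is the best score on the scale and does not mean that the question was inapplicable.

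The sentence also leaves three things open: whether it acts on subjects or on eyes, which visits count, and whether it reaches the slit-lamp measures. Two programmers could build different datasets from it.

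**Working it through.** **No planned figure to reproduce.** The Protocol (VI) and SAP 5 give 33 subjects, 22:11, with no effect size, SD or power. No document gives the share of zero scores. Every zero rate, onset rate and effect below is an assumption.

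**How many measures.** The slit-lamp scales in SAP 13.5.3 are 8 lid + 4 conjunctiva + 8 cornea + 2 anterior chamber = 22; the lens is scored separately. Entry requires only one sign from the list, so many of these may be 0 even in the worse eye.

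**Equal loss in both arms.** A dropped subject has change 0. If a share f is dropped from each arm, full mean = (1 − f) × retained mean, so the raw difference in change is multiplied by 1/(1 − f). At f = 10% this is 1.11; at 16% it is 1.19.

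**Precision.** SE = SD × √(1/n_A + 1/n_P). At 22:11, √(1/22 + 1/11) = 0.369 SD. Power for a 1 SD difference is about Φ(1/0.369 − 1.96) = 77%. Dropping 20%, 60% or 80% of subjects raises the SE to 0.413, 0.584 or 0.826 SD and cuts power to 68%, 40% or 23%.

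**Simulation.** 6000 trials per scenario, 22 against 11, one post-baseline ANCOVA of change on treatment and baseline. Assumed effects (active against placebo) are improvement of 40% against 15%, and onset of 10% against 30% (SANDE) or 5% against 30% (slit lamp). Where improvement or onset is not affected, both arms have the same rate. Non-zero baselines centre on 55 (SANDE, 0–100) and 4 (slit lamp, 0–10).

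| Measure and assumed effect | At 0 at baseline | All subjects | After exclusion | Ratio |
|---|---|---|---|---|
| SANDE fellow eye, improvement and onset | 5% | −13.3 | −13.7 | 1.03 |
| SANDE fellow eye, improvement and onset | 20% | −11.4 | −13.2 | 1.16 |
| SANDE fellow eye, improvement only | 20% | −10.96 | −13.07 | 1.19 |
| Slit lamp, improvement and onset | 50% | −0.66 | −0.97 | 1.47 |
| Slit lamp, improvement and onset | 70% | −0.53 | −0.91 | 1.70 |
| Slit lamp, improvement only | 70% | −0.26 | −0.73 | 2.77 |
| Slit lamp, onset only | 70% | −0.27 | −0.21 | 0.79 |

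- *No effect:* differences stayed near 0. Rejection rates were 0.046–0.056 with the exclusion and 0.035–0.056 without it.
- *Power:* for the slit lamp at 70%, rejection fell from 36% to 18% (improvement and onset) and from 15% to 6% (onset only). For SANDE at 20% with both effects it barely moved, from 63% to 60%.

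**Onset-only row by hand (70% at 0, raw change).** Take a mean new score of 1.5 and a 20% improvement (0.2 × 4 = 0.8) in both arms.

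- All subjects: 0.7 × (0.05 − 0.30) × 1.5 = −0.26.
- Active retained share: 0.7 × 0.05 + 0.3 = 0.335; mean change (0.035 × 1.5 − 0.3 × 0.8)/0.335 = −0.56.
- Placebo retained share: 0.7 × 0.30 + 0.3 = 0.51; mean change (0.21 × 1.5 − 0.3 × 0.8)/0.51 = +0.15.
- Difference after exclusion: −0.71, as simulated.

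The raw difference therefore grows while the ANCOVA difference shrinks. Both analyses are planned.

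**Which visits count.** Only placebo subjects attend Visits 6 and 7. If those visits count, a placebo subject at 0 through Visit 5 can be kept by a later score while an identical active subject is dropped. Assuming 15% of placebo subjects score above 0 there, with no treatment effect, the ANCOVA difference was +0.07, +0.16 and +0.44 at 50%, 70% and 90% zeros. At 90% the rejection rate was 8.9%.

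**The case against.** The strongest reply is that the rule says subjects, not eyes. Read that way, both eyes must be 0 at screening and at every later visit. Entry requires an NIH eye score of at least 2, moderate ocular discomfort and a second moderate symptom, so almost nobody would be dropped from SANDE. The worse eye, which the hypotheses in SAP 2.5 concern, is largely protected on either reading. This stands, and it confines the SANDE concern to eye-by-eye use in the fellow-eye and combined-eye results.

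On the slit lamp, the sentence sits in the SANDE scoring section, speaks of a symptom, and does not appear in the GLIA text as available. The cross-reference in SAP 13.5.3 may mean only the shared model. A reader might take carry-over as stated; it is a literal inference and no more. The slit-lamp measures are also additional variables, and counts of abnormal findings, shift tables and listings are planned alongside the models. That limits the harm but does not settle which dataset the models use.

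On Visits 6 and 7, SAP 6 locks the primary data at Visit 5, so that reading is unlikely for the primary analysis. The sentence itself does not rule it out.

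A reader might also cite "Subjects will be analyzed as randomized" and conclude that the comparison is no longer by randomised group. That sentence concerns arm assignment, and retained subjects keep their arm. The departure is from the membership rule in SAP 7.1.

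**Conclusion.** The concern holds in limited form. The plan states an outcome-dependent exclusion that conflicts with its own analysis population and is not declared as a change. Read per subject, its effect on SANDE is close to nil. Applied per eye, or to slit-lamp signs, it can remove many valid zeros.

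The size rests on assumed rates: about 3–19% for the SANDE fellow eye at 5–20% zeros, and about 1.5–2.8 times for slit-lamp signs at 50–70% when treatment improves existing signs. An onset-only effect gave some shrinkage at 70%. Precision falls as subjects are lost.

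Three stronger readings are not supported:

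- That the rule biases results or inflates type I error outright. With no effect and common visits, neither was seen.
- That differential clearance of symptoms drives the selection. A subject above 0 at baseline is always kept, so only onset can.
- That the treatment difference could be reversed. No calculation here shows it.

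**What to change.** Delete the sentence from SAP 13.2. In 13.2.1 and 13.5.3, state that all modified ITT subjects with a baseline and at least one post-baseline value are analysed, zeros included, and that no zero-based exclusion applies to any eye-level or combined-eye analysis. If subjects or eyes at 0 are of separate interest, define that subset on baseline values only and report its count by arm.

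If the sponsor keeps any such rule, the SAP should say whether it acts per subject or per eye, which visits count and which measures it covers, and list it in SAP 16.

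The cost is one deleted sentence and two short clarifications, with no new data. The estimated mean change may be somewhat smaller because zero scorers are retained. If the rule would have dropped nobody, the results do not change.
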